6.2 Preparation/ handling/ storage/ accountability

6.2.1 Acquisition and accountability

The IMP will be supplied by MC2's designated vendor.

The investigator is responsible for ensuring that all IMP received at the site is inventoried and accounted for throughout the trial. The IMP dispensed to the patient and returned to the site must be documented on the drug accountability form and in the eCRF. All IMP will be stored and disposed of according to the sponsor's instructions.

IMP must be handled in strict accordance with the protocol and the label and must be stored at the trial site in a limited-access area. Used and unused IMP tubes returned by the patient must be available for verification by the trial monitor during on-site monitoring visits.

IMP should be dispensed under the supervision of the investigator or a qualified member of the site staff, or by a hospital/clinic pharmacist. IMP will be supplied only to randomised patients. IMP cannot be relabelled or reassigned for use by other patients. The investigator agrees neither to dispense the IMP from, nor store it at, any site other than the trial sites agreed upon with the sponsor.

Records of trial product used, and dosages administered will be kept during the trial. The trial monitor will note product accountability during site visits and at the completion of the trial. Patients will be asked to return all used and unused tubes in the accompanying box at each visit to ensure drug accountability. All returned tubes (used and unused) will be weighed to determine the amount of IMP used.

6.2.2 Formulation, appearance, packaging, and labelling

Sponsor will provide Solural Pharma with the MC2-25 cream and MC2-25 vehicle. The tubes are identical in appearance and packaging.

MC2-25 cream and MC2-25 vehicle will be labelled in accordance with applicable regulatory requirements and Good Manufacturing Practice Guidelines and delivered to the clinics in boxes.

IMP for one patient consists of the following: One box containing 3 boxes with 8 tubes in each adding up to a total of 24 tubes per patient. Labels for the IMP will comply with the legal requirements of the country where the trial is performed and will be printed in the local language(s).

6.2.3 Product storage and stability

The IMP must be stored securely at the site under the control of the investigator. The temperature will be monitored and documented. The IMP will be supplied to the clinical site(s) as tubes containing 60 g of product. The IMP is to be stored according to the label. At all times, the IMP tube should be protected from direct sunlight exposure.

6.2.4 Preparation and destruction

No preparation of the IMP is needed.

Destruction: IMP must only be destructed after sponsor's approval. Unused IMP (i.e., both dispensed/returned as well as not dispensed IMP) should preferably be destructed locally at the site (to be documented on the IMP destruction form). If the IMP is not destructed at site but returned for destruction, to sponsor's designated vendor, this must also be documented on the IMP return form.

6.3 Measures to minimise bias: randomisation and blinding

Randomization will be performed in a 1:1 ratio. Randomisation data will be kept strictly confidential, accessible only to authorised personnel, until the time of un-blinding.

A patient who fulfils the trial eligibility requirements will be randomly assigned to treatment with IMP.

An external statistician who is independent from the study team will prepare the randomization list using appropriate software tool ensuring equal allocation of patients into the two treatment arms. The external statistician will also prepare the emergency unblinding envelopes. The randomization list will be shared with Solural Pharma (who are responsible for labelling) and with PharmaLex (who are responsible for handling of SAEs) and will be kept strictly confidential, filed securely, and will be accessible only to authorized persons from Solural Pharma and PharmaLex until unblinding. This is a double-blind trial. The sponsor, sponsor representatives, and all patients, monitors, and site staff will be blinded throughout the trial. Instructions for emergency unblinding are provided in Section 10.2.1. The staff at the study treatment manufacturing site and the external statistician responsible for preparing the randomization list are not blinded.

Each patient will be assigned a unique randomization number in ascending order determining which study treatment the patient will receive. These randomization numbers will be based on a supply list accompanying the IMP provided to the sites and the same randomization number (named as kit no. will also be listed to the applicable trial medication. At each dispense, this kit no. will be documented in the eCRF linking the trial medication to correct patient. No patient ID, other than the kit no. will be written on the trial medication.

6.4 Treatment compliance

At all on-treatment visits, the patient will be asked if he/she has used the trial medication as prescribed. Any degree and nature of noncompliance will be specified. In addition, patients will be asked to complete an Application Diary during the treatment period as a measure of treatment compliance. Patients who are consistently noncompliant will be counselled.

6.5 Prohibited therapies

6.5.1 Prohibited therapies prior to baseline

Several therapies are prohibited during the period leading up to baseline as outlined in [Table 3](#). Therapies not listed in the table are allowed.

Table 3: Prohibited therapies prior to baseline

Prohibited Therapy	Exclusion Criterion	Applicable Wash-Out Period Prior to Baseline (Day 0)
Use of anti-cancer treatment	5	3 months or 5 half-lives (whichever is longest)
Start of a new or change of existing non-biologic systemic treatment, including but not limited to corticosteroids, cyclosporin and tacrolimus.	8	21 days
Start of a new or change of existing biologic systemic treatment, including but not limited to etanercept, adalimumab, alefacept, infliximab, and ustekinumab	9	3 months or 5 half-lives (whichever is longest)

Start of a new or change of existing systemic or intravaginal treatment with estrogen containing products	10	21 days
Start of new or change of menstrual care routines	11	21 days
Use of emollients (including but not limited to creams, ointments, oils, or soaps with emollient properties) on the vulvar region Note: Only water and, if necessary, a soap bar without emollient properties, may be used to wash the vulvar region (intimate hygiene) when bathing or showering.	12	3 days
Use of any topical treatment on the vulvar region, including but not limited to calcineurin inhibitors, corticosteroids or anti-infectives.	13	14 days
Use of any light therapy on the vulvar region, including but not limited to UV-B, UV-A and laser.	14	28 days
Received a non-marketed or blinded drug.	15	28 days or 5 half-lives, whichever is longer

6.5.2 Prohibited therapies after Baseline

Use of any therapies that would exclude the participant from participation in the trial (as specified in Section 5.2 Exclusion Criteria) is also prohibited during the treatment and follow-up periods, see [Table 3](#). Therapies not listed in [Table 3](#) are allowed.

6.5.3 Rescue therapies

If prohibited therapies are used as rescue therapies during the screening period, the patient is not eligible for the trial. If prohibited therapies are used as rescue therapies during the treatment period, they must be recorded as concomitant therapies and reported as protocol deviations.

7 Trial intervention discontinuation and participant discontinuation / withdrawal

7.1 Participant discontinuation / discontinuation of trial intervention

In accordance with legal requirements and International Council for Harmonisation (ICH) – Good Clinical Practice (GCP) guidelines, every patient has the right to refuse further participation in this trial (withdrawal from trial) or refuse further treatment (discontinuation of treatment) at any time and without providing reasons. A patient's refusal should be effectuated immediately upon her request.

A patient will be withdrawn from the trial for any of the following reasons:

- Lost to follow-up
- Withdrawal of consent
- Death
- Trial terminated by sponsor

In addition, a patient may be withdrawn from the trial or be discontinued from treatment at any time at the discretion of the investigator.

Reasons for withdrawal from trial or discontinuation of treatment include (but are not necessarily limited to) lack of treatment effect, unacceptable AE(s), pregnancy, and protocol violations.

In the case of trial withdrawal or treatment discontinuation, all assessments of the Week 12 (End of Treatment [EoT]) visit must be performed to the extent possible. The reasons for trial withdrawal or treatment discontinuation must be fully documented in the eCRF and the end of treatment form must be completed when treatment is permanently discontinued, and the end of trial form must be completed at end of the trial or in case of trial withdrawal.

Patients who withdraw from the trial before randomisation will be considered screen failures. After randomisation, in case of treatment discontinuation, the patient should be encouraged to attend remaining trial visits in line with the schedule of assessments (SoA). If a patient is withdrawn from the trial due to an AE or treatment is discontinued due to an AE, the AE must be followed up as outlined in Section 8.8.4.1.

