7.3 End-of-treatment visit

Unless a patient withdraws consent for trial participation, or is lost to follow-up, an End-of-Treatment Visit should be performed as soon as possible (no later than 30 days) after the treatment

has been discontinued. Every effort should be made to conduct the End-of-Treatment Visit before the patient starts subsequent therapy. If a patient is unable to return to the site for the End-of-Treatment Visit, then the patient should be contacted (e.g., by phone) to collect information on AEs and concomitant therapies and other EOT visit assessments (in particular PROs) to the extent possible that occurred within 30 days after the last treatment. Additional information on reporting of AEs can be found in Section 8.8.4.1.

Patients who permanently discontinue treatment at some point after the administration of the first dose of trial medication will not be replaced.

8 Trial assessments and procedures

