8.2 Screening

Up-front waivers for inclusion or exclusion criteria are not allowed. Any deviation from inclusion or exclusion criteria identified post-randomisation, will be reported as a protocol deviation, patients shall continue in the trial as planned unless discontinuation of IMP treatment is warranted for safety reasons.

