8.5.2 Patient reported outcomes (PRO) assessments

8.5.2.1 Worst Itch Numeric Rating Score (WI-NRS) of VLS

The patient's WI-NRS score must be recorded by the patient in a diary once daily (i.e., every day around the same timepoint, e.g. morning, afternoon or evening) for a total of 7 days (i.e. starting 7 days before the next in-clinic visit and ending on the day before the next in-clinic visit) leading up to each in-clinic visit day at Baseline, Week 1, Week 4, Week 8, and Week 12 (or Early Termination) using an 11-point numeric rating scale ranging from 0 to 10:

Please score the intensity of the Worst Itch associated with your lichen sclerosus, that you have experienced in the past 24 hours: 0 (no itch), 1, 2, 3, 4, 5, 6, 7, 8, 9, 10 (worst imaginable itch).

In addition, the patient's WI-NRS score must be reported to the clinical staff at in-clinic visits at Screening 1, Baseline, Week 1, Week 4, Week 8, and Week 12 or Early Termination using the 11-point numeric rating scale above.

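### Protocol 7.1 permits the investigator to end trial follow-up, not only treatment, for lack of effect, adverse events or protocol violations; an early withdrawal of this kind cannot supply the Week 12 itch score that the treatment-policy analysis needs

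*Protocol*

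**What the plan says.** Protocol 7.1 opens with a list of four mandatory grounds, introduced by "A patient will be withdrawn from the trial for any of the following reasons": loss to follow-up, withdrawn consent, death and sponsor termination. It then adds a discretionary route: "a patient may be withdrawn from the trial or be discontinued from treatment at any time at the discretion of the investigator". The reasons for either kind of exit share one open list: "withdrawal from trial or discontinuation of treatment include (but are not necessarily limited to) lack of treatment effect, unacceptable AE(s), pregnancy, and protocol violations". Table 2 (section 2.3.1) offers the same choice, for unacceptable adverse events or lack of improvement, as a mitigation for the vehicle arm.

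On continued follow-up, 7.1 says that "in case of treatment discontinuation, the patient should be encouraged to attend remaining trial visits in line with the schedule of assessments (SoA"). There is no matching request for a patient withdrawn from the trial, and nothing tells the investigator to prefer stopping treatment over ending follow-up.

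At either kind of exit, the Week 12 assessments are to be done as far as possible. Section 7.3 says the visit "should be performed as soon as possible (no later than 30 days) after the treatment" stops, allows patient-reported outcomes to be collected by phone, and adds: "Every effort should be made to conduct the End-of-Treatment Visit before the patient starts subsequent therapy". The seven-day itch diary is requested "leading up to each in-clinic visit day at Baseline, Week 1, Week 4, Week 8, and Week 12 (or Early Termination"), per 8.5.2.1.

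On the analysis side, Protocol 9.4.2.1 and SAP 5.3 set a treatment-policy primary estimand that uses all data whatever the adherence. SAP 4.6.2 (Table 4) assigns visits to analysis time points by study day, with Week 12 running from day 71 to day 91. It says that unscheduled end-of-treatment visits may be taken into account, but no rule moves an early one to Week 12.

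**The concern.** Lack of effect, adverse events and use of prohibited therapy are the events after which a treatment-policy estimand still needs the outcome. If the investigator ends the patient's participation at that point, a Week 12 score that could have been collected is lost.

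The lost value is then imputed within arm from menopausal status, ICIQ-UI-SF score, baseline and preceding visits (SAP 4.7.2). The model has no term for having stopped treatment or used rescue. If most patients stay on treatment, a withdrawn patient is imputed mainly from patients still treated, which is not what treatment policy asks for. Protocol 9.4.2.1 leaves missing-not-at-random analyses optional, and none of the four sensitivity analyses in SAP 5.5.1 is of that kind. The trial also has little power to spare, and 7.3 rules out replacing patients who stop treatment after the first dose.

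**Working it through.** **1. The plan's own power figure.** Inputs from Protocol 9.2: two-sided 5%, effect of 1 SD, 33 patients, 16 to 17 per group, stated power at least 78%. For a two-sample t-test, the noncentrality is δ = d × √(n1 × n2 / (n1 + n2)) on n1 + n2 − 2 degrees of freedom.

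- 16 and 17: δ = √(272/33) = 2.871, power 79.4%.
- 16 and 16: δ = √8 = 2.828, power 78.1%.

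The stated figure is reproduced. It treats every randomised patient as evaluable.

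**2. When can an exit visit count as Week 12?** Study day is days since first treatment plus 1 (SAP 4.4.1), with first application on the Baseline day. The latest exit visit is 30 days after stopping, so the cut-off is 71 − 30 = study day 41. Contact days are those in the Schedule of Assessments, each plus 1. The table applies only to patients who are also withdrawn from the trial.

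| Stop at contact | Study day | Latest exit visit (+30) | Delay needed to reach day 71 |
|---|---|---|---|
| Week 1 | 7–9 | 37–39 | not possible |
| Week 3 (phone) | 17–21 | 47–51 | not possible |
| Week 4 | 25–33 | 55–63 | not possible |
| Week 7 (phone) | 45–49 | 75–79 | 22–26 days |
| Week 8 | 53–61 | 83–91 | 10–18 days |
| Week 11 (phone) | 73–77 | – | none |

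For the Week 7 and Week 8 rows, the delay runs against the instruction to hold the visit promptly and before other therapy starts. An exit value before day 71 is not wasted: it can enter the model at its own analysis visit.

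**3. Power with Week 12 values lost.** The documents give no withdrawal rate, so 1 to 3 lost values are an assumed range. Counting each lost value as a lost patient:

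- 1 lost: 15/17 78.0%; 16/16 78.1%.
- 2 lost: 15/16, δ = √(240/31) = 2.782, 76.7%; 14/17, δ = √(238/31) = 2.771, 76.4%.
- 3 lost: 15/15 75.3%; 14/16 75.1%; 13/17 74.5%.

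These overstate the cost, because the repeated-measures model recovers part of the information from preceding visits. If each lost value still counts as r² of a patient, with r assumed between 0.5 and 0.8 (optimistic in arms this small), two lost values give:

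- r = 0.5, both from the arm of 16: effective sizes 14 + 2 × 0.25 = 14.5 and 17, power 77.2%.
- r = 0.8, both from the arm of 17: effective sizes 16 and 15 + 2 × 0.64 = 16.28, power 78.5%.

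Two lost values therefore cost between 79.4 − 78.5 = 0.9 and 79.4 − 76.4 = 3.0 points.

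**4. Bias.** If m of n patients in an arm are imputed and their true values differ from the imputation by k SD on average, that arm's mean shifts by (m/n) × k. For 2 of 17 and an assumed k of 0.5 to 1, the shift is 0.06 to 0.12 SD; for k = 0 it is zero. Nothing in the documents fixes k or its sign, so this gives scale only.

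**The case against.** The strongest reply is that 7.1 only permits this. It does not direct anyone to withdraw a patient from the trial, it separates the two kinds of exit, and it already asks patients who merely stop treatment to keep attending. That stands. A reader might infer that 7.1 itself produces missing Week 12 data, or that anyone stopping before day 41 is lost to the primary endpoint. The documents support neither: the timing limit applies only to patients also removed from the trial. Nor is the split of contacts a risk measure, since withdrawals need not occur at contacts or be spread evenly over them.

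Several safeguards also narrow the gap. For eligibility deviations, 8.2 says "patients shall continue in the trial as planned unless discontinuation of IMP treatment is warranted for safety reasons". Persistent non-compliance leads to counselling (6.4). Rescue is recorded and reported as a deviation (6.5.3). Section 5.6 sets retention measures. What mainly remains is investigator-led withdrawal for adverse events or lack of effect that goes beyond stopping the cream.

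A reader might further infer that the treatment estimate is biased, or that power must fall below the stated 78%. Neither follows. Bias is about zero if withdrawal depends on the diary scores already observed and no rescue follows. Power stays at about 78% with one loss, and can do so with two if recovery is good. The missing off-treatment term in the imputation model also affects values lost for other reasons, such as withdrawn consent, which a change to 7.1 would not cure.

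Finally, little may be left to gain. Protocol version 4.0 is dated 31 July 2024 and the SAP 30 October 2024, 13 weeks later, against 12 weeks of treatment. The date of the last randomisation is not given, so this suggests, but does not show, that few patients remained on treatment.

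**Conclusion.** The concern holds as a low-cost improvement to consider. The wording allows follow-up to end for reasons after which the primary estimand still needs data, and the exit visit cannot replace the Week 12 score for a trial withdrawal whose treatment stopped before about study day 41. After a stop at Week 7 or Week 8 it can do so only if the visit is delayed.

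The size is modest: about 1 to 3 points of power for two lost values. That rests on an assumed number of losses, a two-sample t approximation and an assumed degree of recovery by the model. The frequency of such withdrawals, and the size and direction of any bias, are unknown. The case for acting is that the value can be collected cheaply, which avoids relying on an assumption that cannot be checked.

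**What to change.** In 7.1, separate the two lists.

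- **Treatment discontinuation only:** lack of effect, adverse events, protocol violations, and use of rescue or prohibited therapy. Ask these patients to stay in follow-up and complete the seven-day diary before Week 12, by phone if needed.
- **Trial withdrawal:** withdrawn consent, loss to follow-up, death, sponsor termination, pregnancy (already mandatory under 8.6.3), and a documented case where continued follow-up would itself be unsafe or impossible, such as loss of capacity.

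Align the mitigation text in Table 2. Leave untouched the patient's own right to withdraw and the investigator's freedom to stop the cream and treat. The burden of staying is small: 10.1.1 notes no blood draws or other procedures considered to carry risk.

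The cost is a short amendment with ethics approval (10.1.2), a note to sites, and a few extra diaries or calls. Benefit in this trial is limited because recruitment has closed at 33. If no patients remain in follow-up, skip the amendment and add a flag for investigator-initiated withdrawal to the disposition-by-reason table already planned in SAP 3.3 and 3.4, which would show whether the problem arose.

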7.2 Lost to follow-up

If a patient is lost to follow-up, every reasonable effort must be made by the site staff to contact the patient and determine the reason for discontinuation/withdrawal. The measures taken to follow-up must be documented.

7.3 End-of-treatment visit

Unless a patient withdraws consent for trial participation, or is lost to follow-up, an End-of-Treatment Visit should be performed as soon as possible (no later than 30 days) after the treatment

has been discontinued. Every effort should be made to conduct the End-of-Treatment Visit before the patient starts subsequent therapy. If a patient is unable to return to the site for the End-of-Treatment Visit, then the patient should be contacted (e.g., by phone) to collect information on AEs and concomitant therapies and other EOT visit assessments (in particular PROs) to the extent possible that occurred within 30 days after the last treatment. Additional information on reporting of AEs can be found in Section 8.8.4.1.

Patients who permanently discontinue treatment at some point after the administration of the first dose of trial medication will not be replaced.

8 Trial assessments and procedures

8.1 Visit schedule

The schedule of assessments (SoA) is provided in [Table 1](#).

The following order of assessments must always be adhered to:

- At Visit 1, the informed consent process must be completed before Patient Reported Outcomes or any other clinical assessment or procedure.
- At all visits, Patient Reported Outcomes should be assessed before all other clinical assessments or procedures.

8.2 Screening

Up-front waivers for inclusion or exclusion criteria are not allowed. Any deviation from inclusion or exclusion criteria identified post-randomisation, will be reported as a protocol deviation, patients shall continue in the trial as planned unless discontinuation of IMP treatment is warranted for safety reasons.

8.3 Demographics and medical history

The following demographic and medical history must be collected:

- Age
- Height (can be self-reported)
- Weight (can be self-reported)
- Race
- Ethnic origin
- Complete VLS history (year of first VLS symptoms, year of VLS diagnosis, diagnosis made by gynaecologist, dermatologist or other [specify], diagnosis confirmed by biopsy, any family members with VLS, currently seeing a VLS treating physician regularly, current VLS treating physician is gynaecologist, dermatologist or other [specify])
- All other current and past medical/surgical conditions within the previous 12 months.

